7.2 Adverse Events

An adverse event (AE) is any untoward medical occurrence in a subject administered a study procedure. An AE can therefore be any unfavorable and unintended sign (including an abnormal laboratory finding), symptom, or disease temporally associated with the use of study procedures. Since this is a study involving an FDA drug, conivaptan, used for approved purposes, exempt from IND regulations, we do not anticipate adverse events to be a common occurrence in this research study.

In case of such occurrence, for all AEs, the investigator will obtain adequate information to determine the following:

- The appropriate descriptive term
- Severity

NSJC-1601
V6APR2018

- Onset/resolution dates and outcome.
- Causality: the relationship of each AE will be defined as “unrelated” or “related” to study procedures:
Unrelated: There is little or no possibility that the study procedures caused the AE;
Related: There exists at least a reasonable possibility that the study procedures caused or contributed to the AE; an inability to identify an alternate etiology for an AE should not, by itself, justify a “related” attribution.
- Whether it meets the criteria for classification as a SAE.

7.3 Serious Adverse Events

An SAE is any AE from this study that results in one of the following outcomes:

- Death
- Requires initial or prolonged inpatient hospitalization
- Is life-threatening (that is, immediate risk of dying).
- Is a persistent or significant disability/incapacity.
- Other significant medical hazard.

7.4 Adverse Events Reporting

The investigator will document all directly observed AEs and all AEs spontaneously reported by the study subject. SAEs will also be reported to regulatory authorities in accordance with all applicable regulations, as appropriate.

8. Data Management

8.1 Data Reviewed

- Demographics: Age, race, gender, and risk factors (hypertension, diabetes, illicit drug use, coronary artery disease, stroke, alcohol use).
- Clinical Grading Scores:
 - Outcome: mRS (Appendix 2) at baseline and discharge (if available). This can be performed by study team or as part of normal clinical practice.
 - ICH score at baseline (Appendix 5).
 - GCS score at baseline, 24 hrs from enrollment, 72 hrs from enrollment 7 day and discharge (if available) (Appendix 4).
 - APACHE II at baseline (Appendix 3).
- Duration of Neruo-ICU and hospital stay.
- Need for any of the following:
 - EVD/Bolt.
 - Hemi-craniectomy.
 - Central venous line/PICC/Arterial line.
 - RRT.
- Concomitant osmotherapy:
 - Hypertonic saline. The total mEq delivered and form of delivery (i.e. NS vs. 3% NaCl solution vs 23.4% NaCl solution.)
 - Mannitol. Number of doses and total grams received.
- Concomitant medications
- Imaging evaluation: CT scans will be dichotomized and ICH volume and CE volume will be compared over time. The individual summed and averaged volumes, net ICH volume and edema volumes will be compared. A board certified/eligible radiologist will calculate serially

the hemorrhage volume on CT during the study period. ICH volume will be serially assessed both by the $(Ax \times B \times C)/2$ method and by volumetric calculations using volumetric software. Serial assessments of edema will occur by measurements of the length and width of regional edema in the CT slice demonstrating the greatest amount of edema. Volumetric calculations using volumetric software will also be employed to evaluate for CE volume. Further, the same measurements one slice above and below will be performed to allow for a volumetric comparison. Completed CT scan measurements and calculations will be e-mailed to the research coordinator for data entry. In addition to the planned imaging and chemistry panels, any other imaging or basic laboratory work, deemed medically necessary for patient care outside the study, will be evaluated in the final analysis.

Clinical data collected from time of ICU admission to day 7:

- Vital signs (BP, HR, Temp)
- Daily weights and admission height
- ICP/ CPP values- when available/when a monitor is being used
- CVP values- when available
- Volumes for intake and output.
- Na⁺ values
- Cl⁻ values
- Cr values
- BUN values
- PO₂ values- when available
- PCO₂ values-when available
- A-a gradient- when available
- Urinalysis results-when available
- All culture results

Data sources will include medical records, lab results, device reports, and vital signs. Information from Excellian will need to be obtained within a couple days of the patient leaving the Neuro-ICU.

We have the support of the Neuro-ICU nurses/personnel through the Neuro-ICU unit manager [name]. The research coordinator will stop by each subject's room 1-2x/day during the patients study duration to confirm safety assessments are being monitored, and to collect data and information.

8.2 Data Entry & Database Completion

All completed data collection forms will be sent to the data entry person for entry into the study database.

All paper forms will be stored in a locked cabinet, with only the study personnel knowing the location of the key.

All database & study computers will be password-protected, with only the study team members knowing the password.

Following completion of the database, random data validation by manual re-entry will occur to ensure the accuracy of previous data and information entry.

NSJC-1601
V6APR2018

All patient identifiers will be deleted. Electronic data will be stored in a protected server accessible only to team members. Paper forms will be stored in a locked file in the PI's JNNI office. Upon completion of the study, all paper forms will be destroyed.

The completed & validated de-identified database will then be delivered to the biostatistician for statistical analyses to be performed.

8.3 Data Sharing

- 1) The results obtained from this study will be prepared within a manuscript for submission to a peer-reviewed journal.
- 2) The results will also be used as preliminary data for future studies, including a rigorous, controlled study of the efficacy and safety of conivaptan compared to traditional treatments/a phase II dosing study.

9. Statistical Analysis

Descriptive statistics will be used to summarize the baseline characteristics and the outcomes, such as adverse events and the hospital length of stay. In addition, Mixed model with unequally spaced repeated measures will be performed to evaluate the change of the variables with unequally spaced repeated measures, such as edema content, ICH score, GCS score, and APACHE II score, where unequally spaced repeated edema content measurements for 7 patients will be plotted; while Mixed model with equally spaced repeated measures will be performed to analyze the change of the variables with equally spaced repeated measures, such Mg and PO₄.

10. Study Oversight

The PI and the research team will be responsible for all safety assessments. Safety will be assessed for all patients enrolled in an ongoing fashion based on the incidence of AEs, SAEs, and treatment discontinuations due to AE. If any significant safety issues arise, a decision to modify or terminate the trial will be made. If requested, the study will be made available for monitoring, auditing, IRB review, and regulatory inspection by providing direct access to study related source data to oversight bodies like FDA.

11. IRB Review/Ethics/Informed Consent

ICH GCP guidelines require that all investigational studies be conducted under the auspices of an IRB/EC. This committee will approve all aspects of the study, including the protocol and informed consent to be used and any modifications made to the protocol or informed consent. The investigator will retain a copy of the communication from the IRB/EC to the investigator indicating approval/favorable opinion of the protocol and consent form. All changes to the protocol or consent form will be reviewed and approved prior to implementation, except where necessary to eliminate apparent immediate hazards to human patients. The investigator will also be responsible for obtaining periodic IRB/EC re-approval throughout the duration of the study. Copies of the investigator's periodic report to the IRB/EC and copies of the IRB/EC's continuance of approval will be retained in the site study files.

A sample informed consent form will also be provided to the IRB/EC. Prior to the beginning of the study, the investigator will obtain the IRB/ECs written approval/favorable opinion of the written Informed Consent Form and any other written information to be provided to patients. The written approval of the IRB/EC together with the approved subject information/Informed Consent Forms will be filed in the study files. The Informed Consent Form will contain all elements required ICH Good Clinical Practices (GCP) Guidelines in addition to other elements required by federal, state, local or institutional policy. The investigator will be responsible for obtaining an Informed Consent signed by each subject or his/her legally authorized representative, prior to his/her participation in the study, in accordance with ICH GCP guidelines. Informed Consent will be obtained from a subject or his/her legally authorized representative after a full explanation of the purpose of the study, the risks and discomforts involved, potential benefits, etc., have been provided by the investigator or designee, both verbally and in writing. The investigator is responsible to see that informed consent is obtained from each subject or legal representative and to obtain the appropriate signatures and dates on the informed consent document prior to the performance of any protocol procedures. Participation in the study and date of informed consent given by the subject will be documented appropriately in the subject's files.

Complicating ICH is the development of cerebral edema (CE). Worsening CE has been implicated in delayed neurological deterioration, and worse patient outcomes, largely due to the elevation of intracerebral pressure (ICP). Elevations in ICP reduce the ability of blood to reach the brain, exacerbating the injury and producing ischemia. Reduction of this edema may reduce the degree of neuronal death, decreasing hospital length-of-stay (LOS), and improving short-term outcomes.

Wide variability exists in the treatment of ICP and CE among intensivists. The use of mannitol, which elevates the osmolarity within the cerebral vasculature, promoting water movement across the blood-brain barrier and into the capillary system, is common, but is limited by its deleterious effects on renal function, fluctuations in intravascular volume, and pH. Most concerning is the slow elimination of mannitol from the cerebrospinal fluid (CSF), which may potentially require progressively higher doses, over time to control ICP, and may result in rebound CE. Increasingly, hypertonic saline (HS), which acts similar to mannitol, is being used to abate CE. However, this therapy has not demonstrated any survival or outcome benefit despite reductions in ICP. A retrospective review of available data at Henry Ford Health System preliminarily demonstrates adverse effects on renal function with the use of HS. Further, anecdotal observations have noted changes in renal function and difficulty replacing free-water deficits (FWD) following aggressive antecedent use of HS. A known side-effect of HS therapy is hyperchloremia (HC). Chlorine is a potent renal vasoconstrictor, thus potentially reducing blood flow, precipitating renal ischemia, and reducing glomerular filtration rate. Finally, the use of HS may be associated with increased risk of blood-stream infections (BSI), and trends to increased risk of nosocomial and urinary tract infections (UTI).

In sum, neurocritical care needs a safer alternative therapy that can reduce the development of CE, potentially decreasing ICU LOS and possibly improving outcomes. Conivaptan, a non-selective Arginine-Vasopressin (AVP) V_{1A}/V_2 antagonist, reduces the production of aquaporin-4 (AQP4) production, the predominant class of water channel in the brain, thus promoting aqueresis. Conivaptan is approved for the treatment of euvolemic and hypervolemic hyponatremia. This mechanism of action suggests that conivaptan could potentially be used clinically to reduce CE. Current clinical data in traumatic brain injury (TBI) patients demonstrate conivaptan is safe and well tolerated using a single dose to increase sodium (Na^+) in a controlled fashion to reduce ICP. Further, additional work has demonstrated the safety and tolerability of conivaptan in doses ranging from 10-80 mg/day in the neurocritical care population. Recently, bolusing of conivaptan (20 mg) has been shown to lower ICP in hyponatremia following TBI and cerebral ischemia. The authors reported improvements in cerebral perfusion pressure (CPP) and stable blood pressure, and a prolonged reduction in ICP. They theorize that the antagonism of V_2 by conivaptan promotes free water loss to reduce brain water content (BWC), while the antagonism of V_1 antagonism may improve

cerebral blood flow (CBF) and reduce blood brain barrier permeability.

Given the enormous costs of ICH, problems with current therapies, and variability in treatment, there is an urgent need to identify a therapy that has a better safety and effectiveness profile than the currently used agents. Our central hypothesis is that through reductions in AQP4 expression, the early use of conivaptan will reduce CE while also being safe in the ICH population. Our long term goal is to show that early use of conivaptan in ICH will reduce CE, thus improving outcomes and reducing the need for rescue therapies, ICU LOS, and overall treatment cost. The objective of this proposal is to first establish whether conivaptan use, at a dose currently determined as safe (40 mg/day), can reduce CE. This is an essential first step in understanding the role of conivaptan in CE management. If this proof-of-concept study demonstrates the desired effect, work can take place identifying the optimal dosing and frequency needed for maximal effect.

3. Study Objectives and Endpoints

Study Objectives

The study population consists of patients with ICH at risk for developing CE.

a. Primary Objective – Safety and Tolerability

An evaluation of the safety assessment parameters of each of the seven (7) subjects will be done by the PI and Co-I during the patient's care. Should events occur regarding the administration of conivaptan that raise safety concerns, the PI has the authority to withdraw the subject and/or halt the study pending further investigation.

b. Secondary Objectives

Several secondary hypotheses can be tested for data generated by this investigation:

1. Reduction in CE as measured on CT. Goal is a 5-10% reduction in CE over time.
2. Patient outcomes: the modified Rankin Scale (mRS) will be used to assess patient outcomes at hospital discharge. This scale assess functional deficits on a scale from 0 (no deficit) to 6 (death).
3. Cost of care: Several proximal measures will be used to assess cost, including length of stay in the ICU, the need for EVD/bolt or surgical procedures to reduce or manage CE, the need for lines (central venous, arterial, PICC) or tracheostomy/PEGs, and the number of patients that required ventilation.

Study Endpoints

1. Laboratory values: assessment will end at the completion of conivaptan administration (Day 3).
2. Long-term Outcome: Patients will be observed for three months, beginning at enrollment, to determine long-term outcomes of conivaptan treatment.

4. Investigation Plan

This a single-center, open-label prospective study which aims to evaluate the safety and tolerability of conivaptan in patients with ICH that are at risk for developing CE. The study will include 7 patients with a diagnosis of ICH that is ≥ 20 cc in volume, aged between 18 – 80 years. All patients will receive 20mg IV of conivaptan every 12 hours equaling 40mg/day over 2 days (4 doses total), in addition to the standardized ICH management.

All observations and assessments will be conducted as displayed in Table 1 of the Protocol. Patients will have CT scans at baseline and ~24, 72, and 168 hours (7 days) from enrollment to check for bleeding, lasting edema, or rebound edema. An 8 hour variance is permitted. It is preferable that the CT scans be done at 3mm increments as this is helpful for volume analysis, but 5mm is acceptable. Further imaging is left to the discretion of the treating/primary service physician. Electrolytes (standard-of-care, basic metabolic panel) for all subjects/patients will be measured every 12 hours for the first 72 hours of the study, and then daily after 72 hours. This is considered a regular schedule based on clinical need. However, during the ~48 hour period when the subjects are receiving conivaptan, a comprehensive metabolic panel, Mg, and PO₄ will be drawn and analyzed 6 hours after each conivaptan dose. These labs may be done sooner based on the patient's progress/need and/or the attending physician's direction. Neurological exams (e.g., EEGs), vital signs, and urine output measurements will be conducted as per Neuro-ICU protocol. The need for ancillary monitoring tools (i.e. EVDs, bolts, microdialysis, EEG, near-infrared spectroscopy) will be at the discretion of the treating physicians. Subjects will return for a 3 month follow-up assessment to assess neurological function and a final CT scan.

Study Duration: Each subject is expected to participate in the study for 7 days (including medication administration and wash-out) and the 3-month follow up.

Inclusion Criteria

- Age ≥ 18 years old and < 80 years.
- Diagnosis of primary ICH ≥ 20 cc in volume.
- Enrollment within 48 hours from initial symptoms.
- Signed informed consent from the patient or obtained via their legally authorized representative (if the patient is not able to sign the informed consent themselves). The patient's decisional capacity to either provide or refuse consent will be determined using the Glasgow Coma Scale (GCS), which is being assessed at baseline and at 24 hours (+/- 6hrs) after enrollment. A potential study participant with a GCS > 14 will be asked to provide their own initial study consent. A GCS ≤ 14 would indicate the need to pursue consent via legally authorized representative. Patient and/or LAR must be English speaking.

Exclusion Criteria

- Current need for renal replacement therapy (RRT).
- GFR of <30 mL/minute at time of admission.
- Participation in another study for ICH or intraventricular hemorrhage.
- ICH related to infection, thrombolysis, subarachnoid hemorrhage, trauma or tumor.
- Presence of HIV or active fungal infection that is known based on information in the EMR.

- Continued use of digoxin or amlodipine (as recommended by the manufacturer due to CYP3A inhibition).
- Active hepatic failure as defined by AST >160 units/L and/or ALT >180 units/L, or total bilirubin levels greater than four times normal levels (>4.8mg/dL).
- Serum Na⁺ ≥ 145 mmol/L (admission labs or any time prior to recruitment/enrollment).
- Unable to receive conivaptan based on contraindications indicated by the manufacturer.
- Pregnant or lactating females.
- Not expected to survive within 48 hours of admission, or a presumed diagnosis of brain death.

5. Statistical Methods

5.1: Study Subjects and Analysis Sets

All enrolled patients will be included in a single analysis set and data will be summarized using frequencies and percentages.

5.2: General Methodology

This study is looking to preliminarily evaluate the safety, tolerability, and efficacy of conivaptan treatment. Unfortunately, it is not powered to provide robust statistical evaluation of safety and tolerability, nor to detect differences in efficacy between subjects. As such, all analysis will be descriptive in nature. Categorical variables will be summarized using counts and percentages. Continuous variables will be summarized using descriptive statistics: number of patients, mean, median, and full range, as appropriate.

Statistical analysis will consist of:

- Descriptive analysis of patient characteristics
- Frequency of relevant complications and medical interventions
- Changes in CE volume

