Protocol

CONIVAPTAN FOR THE REDUCTION OF CEREBRAL EDEMA IN INTRACEREBRAL HEMORRHAGE – A Safety and Tolerability Study

NSJC-1601 NCT03000283

Funded by United Hospital Medical Education and Research Committee

Principal Investigator: [name]

Co-Investigators: [name]
[name]
[name]

Research Nurse: [name]

Study Coordinator: [name], BS
[name], BA, CCRC

United Hospital, part of Allina Health
John Nasseff Neuroscience Institute, part of Allina Health
[name]
[name]
[contact]

TABLE OF CONTENTS

Section	Page
1. Research Goal	3
2. Specific Aims	3
3. Background	3
4. Significance	5
5. Preliminary Studies and/or Data	6
6. Research Design and Methods	6
6.1. Study Design	6
6.2. Inclusion/Exclusion Criteria	6
6.2.1. Inclusion Criteria	6
6.2.2. Exclusion Criteria	7
6.3. Subject Recruitment	7
6.4. Sample Size	7
6.5. Study Testing Location	8
6.6. Consent and Enrollment Process	8
6.7. Why a patient should participate in this trial	9
6.8. Treatment with Conivaptan	11
6.9. Primary Assessments	14
6.10 Secondary Assessments	15
7. Safety Variables	15
7.1. Risks and Benefits	16
7.2. Adverse Events	16
7.3. Serious Adverse Events	17
7.4. Adverse Events Reporting	17
8. Data Management	17
8.1. Data Reviewed	17
8.2. Data Entry & Database Completion	18
8.3. Data Sharing	19
9. Statistical Analysis	19
10. Study Oversight	19
11. IRB Review/Ethics/ Informed Consent	19
12. Confidentiality	20
13. References	20
14. Appendices	24

1. Research Goal

The goal of this study is to preliminarily determine/estimate feasibility and whether frequent and early conivaptan use, at a dose currently determined to be safe (i.e., 40mg/day), is safe and well-tolerated in patients with cerebral edema from intracerebral hemorrhage (ICH) and pressure (ICP). A further goal is to preliminarily estimate whether conivaptan at this same dose can reduce cerebral edema (CE) in these same patients. This study is also an essential first step in understanding the role of conivaptan in CE management.

Hypothesis: The frequent and early use of conivaptan at 40mg/day will be safe and well-tolerated, and also reduce cerebral edema, in patients with intracerebral hemorrhage and pressure.

2. Specific Aims

Aim 1: Evaluate the feasibility of the proposed study methods.

Subaim 1: Determine the efficiency of enrolling patients into the study. [Accomplished by tracking the number of patients asked to participate compared to the number of subjects enrolled into the study.]

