6.4 Sample Size

This study is looking to preliminarily evaluate the safety, tolerability, and efficacy (presence of moderate reduction in CE), and as a ratio of ICH volume to CE volume. Unfortunately, it is not powered to provide robust statistical evaluation of safety and tolerability, nor to detect differences in efficacy, due to time and budgetary limitations.

Seven (7) patients will be treated with conivaptan (40mg/day; four 20mg doses over a 2 day period) in addition to conventional medical means. This number of patients takes into account information in the conivaptan in TBI patients study by Galton et al (2011), use of glyburide in ICH by Sheth et al. (2014), as well as time and budgetary limitations.

The goal is to enroll all seven (7) patients within an 18-month period. This recruitment goal should be achievable since:

- 1) according to the PI's experience, (based on 2015 data) ~50-70 ICH patients (ICD-10-CM code 161.9) are admitted per year to United Hospital and
- 2) according to a recent electronic feasibility search, in the year 2015, 55 patients with a diagnosis of ICH were admitted to United Hospital. Of these patients, the PI determined that 9 would have been eligible for the study, based on the study's inclusion and exclusion criteria.

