6.10 Secondary Assessments (Effectiveness)

- Reduction in CE as measured on CT. Goal is a 5-10% reduction in CE over time. Reduction will be measured both as absolute reduction, and as relative reduction, comparing the ratio of ICH to edema volume. The absolute edema reduction is more clinically relevant, while the ratio of ICH to edema volume has more research relevance, to aid in designing the next related studies.
- Outcome. mRS (Appendix 2) at discharge from ICU and from hospital stratified by APACHE II (Appendix 3), GCS (Appendix 4), and ICH Score (Appendix 5)
- Cost
 1. Length of stay in the neuro ICU.
 2. Need for EVD/bolt or surgical procedures (craniectomy, clot evacuation, VPS) for reduction/management of CE.
 3. Need for central venous lines, arterial lines, PICC lines, tracheostomy/PEGs.
 4. Duration on ventilator.
 5. Duration of EVD/bolt.

7. Safety Variables

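### SAP 5.2 plans no confidence interval for safety proportions and no SD or interval for edema change, although the study sets out to estimate both and to inform later trials

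*SAP*

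**What the plan says.** Protocol 6.4 fixes the size: "Seven (7) patients will be treated with conivaptan". It bases that number on two earlier studies "as well as time and budgetary limitations", with no alpha, power, effect size or SD. SAP 5.1 sets the denominator: "All enrolled patients will be included in a single analysis set".

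SAP 5.2 then gives the summary methods. For events: "Categorical variables will be summarized using counts and percentages". For continuous variables: "number of patients, mean, median, and full range, as appropriate". It lists change in edema volume among the analyses, treats every analysis as descriptive, and says of the study that "it is not powered to provide robust statistical evaluation of safety and tolerability". SAP 5.3 judges safety by how many patients have events, and repeats that evaluation is descriptive because numbers are small and there is no control group.

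The aims are set out in the protocol. The hypothesis in section 1 reads: "The frequent and early use of conivaptan at 40mg/day will be safe and well-tolerated". The goal stated just before it is more cautious and speaks of preliminary estimation. Aim 2 in section 2 is to estimate trends in safety, tolerability and efficacy. Section 6.10 says the ratio of hemorrhage to edema volume is "to aid in designing the next related studies", and section 8.3 says more generally that the results will be preliminary data for a controlled or phase II dosing study. Section 9 plans a mixed model for the irregularly timed edema measurements and a plot of them for the 7 patients. The SAP mentions neither.

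**The concern.** An estimation aim calls for an estimate and a statement of how uncertain it is. SAP 5.2 supplies only the estimate. That the study is unpowered and descriptive does not excuse the gap: an SD or an interval is itself a description and needs neither power nor a control group.

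Two things are at stake.

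- **Safety, the primary objective.** The main output will be counts out of 7. A table line of 0 (0%), next to a hypothesis that the drug is safe, does not tell the reader which event rates remain possible.
- **Edema.** The goal is a 5–10% reduction, and the results are to feed later designs. Whoever designs the next trial needs the spread of within-patient change and a sense of how well it is known.

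**Working it through.** The documents state no interval or SD, and the sample size has no statistical derivation, so there is no figure of the plan's own to reproduce. The steps below show what the missing summaries would say.

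**Inputs.** n = 7 (protocol 6.4; SAP 5.1 if all 7 are enrolled and evaluable). Seizures in 15–20% of ICH patients (protocol 6.9). 30-day mortality about 40% (protocol section 3). Edema goal 5–10% (protocol 6.10, SAP section 3). The 95% level is an assumption; the documents give none.

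**1. Exact (Clopper-Pearson) limits for event counts.** For 0/7 the two-sided 95% upper limit is 1 − 0.025^(1/7) = 0.410. The one-sided 95% limit is 1 − 0.05^(1/7) = 0.348.

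| Events | Percent | Exact two-sided 95% CI |
|---|---|---|
| 0/7 | 0.0 | 0 to 41.0 |
| 1/7 | 14.3 | 0.4 to 57.9 |
| 2/7 | 28.6 | 3.7 to 71.0 |

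**2. Chance of seeing no event, (1 − p)^7.**

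- p = 0.10: 0.90^7 = 0.48
- p = 0.15: 0.85^7 = 0.32
- p = 0.20: 0.80^7 = 0.21
- p = 0.40: 0.60^7 = 0.028

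So no seizures in 7 patients would be unremarkable at the protocol's own background rate and could not show that the rate is below it. The 40% line shows that a zero is not always uninformative. That mortality figure is a poor benchmark here, though, because patients not expected to survive 48 hours are excluded.

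**3. Precision of a mean edema change.** The half-width of a t-based 95% interval is t(0.975, 6)/√7 × SD = 2.447/2.646 × SD = 0.925 SD. If the 5–10% goal is read as percent change within patient (the documents do not define the scale), the half-width is below 5 or 10 points only when the SD is below 5/0.925 = 5.4 or 10/0.925 = 10.8 points.

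**4. Precision of the SD itself.** With 6 degrees of freedom the 95% limits for the true SD are √(6/χ²) times the observed SD, which gives factors of 0.644 and 2.202. A later sample size scales with the SD squared, so the factors on it are 0.42 and 4.85. Illustration: a 10-point difference, 80% power, two-sided 0.05, n per arm = 2 × (1.960 + 0.842)² × (SD/10)². The SDs are assumed.

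| Assumed SD (points) | n per arm | n per arm across the 95% limits of the SD |
|---|---|---|
| 20 | 63 | 27 to 305 |
| 30 | 142 | 59 to 686 |
| 40 | 252 | 105 to 1218 |

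**5. What the planned range already gives.** For normal data at n = 7 the expected range is 2.704 SD, so range/2.704 estimates the SD. In 1,000,000 simulated samples the range had a coefficient of variation of 31%, against 29% for the sample SD, and the two correlated at 0.95. This helps only if the range is reported for the change in edema, not just for the volume at each visit.

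**The case against.** The strongest reply is that little information is lost. A count with its denominator of 7 fully determines the exact interval, so any reader can compute it. The range yields an approximate SD almost as precise as the sample SD if the data are roughly normal. Protocol section 9 adds a mixed model, which would give variance components, and a plot of the 7 patients' edema. All of this stands. A reader might infer that the pilot leaves no usable variance; the documents do not support that. What remains is that the range rests on the two most extreme patients, and that the SAP carries forward neither the model nor the plot.

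A second reply is that nothing in the plan equates 0/7 with safety. That also stands. A reader might infer that the plan would declare the drug safe on a zero count. No such rule exists, protocol 6.4 and SAP 5.2 both say the study is unpowered, and SAP 5.3 says evaluation is descriptive. Misreading is a risk of presentation. The general caveats say that the study is small, but not which event rates the data exclude.

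Third, the remedy has limits. An SD from 7 patients is itself imprecise (step 4). An interval for edema change compared with zero is not a test of the drug either: there is no control, and protocol 6.7 puts the edema peak at 7–14 days while the planned in-hospital scans end at day 7, so no change is not the natural reference. Both points stand and belong in the fix as stated cautions. They do not argue for leaving the SD and interval out.

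**Conclusion.** The omission is real: the SAP plans neither an interval for the safety proportions nor an SD or interval for edema change, and the protocol names none. It is a reporting gap of minor severity, not an error in any stated figure, and closing it is a cheap improvement. Its practical weight lies in the primary objective. With 0/7, rates up to 41.0% remain compatible with the data, and such a zero arises with probability 0.32 to 0.21 at the 15–20% seizure rate that the protocol cites.

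The figures assume 7 evaluable, independent patients and a chosen 95% level. The SD factors, the t interval and the range conversion also assume roughly normal data. Measures available only in some patients, such as ICP, would have fewer than 7 and wider intervals. Separately, the mixed model in protocol section 9 and the purely descriptive analysis in SAP 5.2 do not agree and need reconciling.

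**What to change.** In SAP 5.2:

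- Add an exact (Clopper-Pearson) two-sided 95% CI for the key safety proportions, naming which events these are and stating that 95% is a choice. For 0/7 the table would show 0 to 41.0% (one-sided 95% upper limit 34.8%).
- Report the SD and a t-based 95% CI for within-patient edema change, on a stated scale (absolute volume, percent change or ratio). Add three notes: the interval assumes rough normality; an SD from 7 patients is known only to within 0.64–2.20 times; and without a control the interval does not measure a drug effect.
- Word the safety conclusion as the event rates that the data exclude.
- Reconcile with protocol section 9: either carry the mixed model and the plot of the 7 patients' edema into the SAP, or record that they are dropped and why.

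The cost is a few table columns and conclusions that look less favourable. No extra patients, visits or measurements are needed.
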